9. STUDY PROCEDURES

a) Provide a detailed description of all study procedures and intervention(s) each subject and/or cohort will experience. Provide a schedule of visits and the procedures that occur at each visit (e.g., tests, questionnaires, surveys, imaging or other interventions.). If the study also involves standard of care, differentiate between research only procedures and standard of care.

Response:

Determine the clinical response of SD and SD/VT symptoms to sodium oxybate using a double-blind, placebo-controlled, randomized, cross-over study design.

The experimental design includes (1) screening for study eligibility; (2) an objective standardized alcohol challenge test for assessment of symptom responsiveness to alcohol, and (3) a double-blind, placebo-controlled, randomized, crossover study of sodium oxybate. The **primary outcome** will be to determine the response of SD and VT symptoms to sodium oxybate 40 min after administration, compared to placebo. We will recruit the following groups of patients:

- (1) ETOH+ SD and SD/VT who report positive effects of alcohol on their voice symptoms;
- (2) ETOH- SD and SD/VT who report no effects of alcohol on their voice symptoms, and Although our prior studies have shown that sodium oxybate has similar effects in both SD and SD/VT patients as well as in ADSD and ABSD, the inclusion of these patients will allow to capture the entire SD populations and to cross-validate our findings. On the other hand, the inclusion of negative controls with ETOH- SD and ETOH- SD/VT will allow for enhanced explanations of our findings and delineation of the primary factors contributing to the pathophysiology of SD and VT with respect to treatment outcome.

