Randomization and Allocation. Following the alcohol challenge, patients will be randomized for the double-blind, placebo-controlled, cross-over study. The randomization will be performed by the MEEI Research Pharmacy and will be blinded for the investigators and patients. The study will be conducted under the existing Investigational New Drug (IND) application granted to the PI by the US Food and Drug Administration (FDA) for the use of sodium oxybate in SD and SD/VT patients (#117,954). Patients will be allocated 1:1 to a treatment sequence #1 of sodium oxybate/placebo or sequence #2 of placebo/sodium oxybate. Jazz Pharmaceuticals, Inc., will provide sodium oxybate and the matching placebo for research purposes, which will be sent directly to the MEEI Research Pharmacy. The placebo will be a clear solution with salty taste that matches the appearance and taste of the drug. Sodium oxybate (1.5 g = 3 ml) of oral solution diluted in 47 ml of water) and the placebo (50 ml) will be formulated in sequentially numbered containers by the research pharmacy in the morning of administration. Both patients and investigators will be blinded until all outcome data are processed and the database is locked at the end of the study. EPIC will be used for study drug dispensing to ensure accurate and complete documentation.

Study drug will be administered by a licensed physician associated with this protocol.

As stated above under the *General Study Procedures* section, all patients will be assessed for their vital signs, MoCA, C-SSRS, side effects, and sleepiness immediately before and 45, 180, 300 min after drug/placebo intake. As a primary outcome measure, voice and speech recordings will be performed at the same time points. Data will be de-identified, randomized, and blindly rated for symptom severity, as described above. Our prior studies have shown that the effects of sodium oxybate (1-1.5 g) in ETOH+ movement disorders are obvious 30-45 min following drug intake and last approximately 3.5-4 hours (Frucht et al., 2005a; Frucht et al., 2005b; Arpesella et al., 2009; Simonyan and Frucht, 2013; Rumbach et al., 2016).

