10. STUDY OUTCOMES

a) **Primary Outcome Measure(s)** - describe how you will measure the primary and other outcomes of the study (e.g., blood pressure change, changes in visual acuity using a specific test, pain scales, responses on a questionnaire, etc.). Upload copies of your data collection tools and/or a list of all variables/data points you will collect.

Note: Primary outcome measures may be measured in various ways such as:

- binary (e.g. improvement in symptoms vs. no improvement in symptoms)
- continuous (e.g. weight kg, blood loss mL)
- ordinal (e.g. pain mild, moderate, severe)
- time to event (e.g. survival)
- counts (e.g. number of infections, number of events occurring)

Response: Primary outcome measures will include clinical improvement of voice symptoms.

b) Describe any secondary or other outcomes (exploratory): N/A

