12. STATISTICAL METHODS

Describe the planned statistical methods including specific tests (e.g., parametric and non-parametric tests, estimation of incidence and prevalence rates, odds ratios, survival/failure analyses, intent to treat analyses). Provide the power calculations used to estimate the proposed sample size. If needed, please consult a biostatistician. (Note: Biostatistical consults are available through Harvard Catalyst.)

Response:

Audio recordings will be de-identified, randomized and blindly rated to count the voice breaks as well as to quantify harshness, breathiness, tremor, and hoarseness using a visual analog scale with three gradation indicators along a 100-mm line (normal, modulates voice, offsets voice), with distance in mm denoting the degree of deviancy from normal, as described earlier (Kirke et al., 2016). Alcohol Challenge Test. All individual measures before and after alcohol intake will be compared using the equation ((Baseline-Alcohol Challenge)/Baseline) \times 100%. To account for potential subjective bias and ensure reliable alcohol effects on voice symptoms, we will consider patients with \geq 10% change of their symptoms from baseline as responsive to alcohol (ETOH+) (Haubenberger et al., 2013; Voller et al., 2014). As a secondary outcome, we will compute Pearson's correlations between symptom scores and brAC measures to examine the baseline and each time point in respect to alcohol content at a corrected p \leq 0.05.

Analysis. The primary outcome within each group will be examined using a linear mixed effect model with treatment (sodium oxybate and placebo) and treatment visits as interacting fixed effects and a per subject random effect at overall $p \le 0.01$ to correct for multiple comparisons. If the interaction between the fixed effects is significant, the difference between treatments will be tested using linear contrasts of least-squares means for the fitted model at $p \le 0.05$ adjusted for multiple comparisons. As a secondary analysis, benefit ratio will be calculated as (sodium oxybate effect – placebo effect) and analyzed using a Friedman test at $p \le 0.01$.

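### The secondary oxybate-minus-placebo benefit measure is given a Friedman test with no stated conditions or null; on the post-dose differences that test asks whether the difference varies over time, not whether it differs from zero

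*Combined protocol and SAP*

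**What the plan says.** The whole specification is one sentence in Section 12 of the combined protocol and SAP: a "benefit ratio will be calculated as (sodium oxybate effect – placebo effect) and analyzed using a Friedman test" at p ≤ 0.01, as a secondary analysis.

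The details that the sentence leaves out are not supplied elsewhere:

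- Section 10b gives no definition: "Describe any secondary or other outcomes (exploratory): N/A". The secondary-hypotheses item in Section 11b has no response.
- Section 9a schedules assessments, ending with "sleepiness immediately before and 45, 180, 300 min after drug/placebo intake", and adds: "As a primary outcome measure, voice and speech recordings will be performed at the same time points". It does not link these times to the Friedman test.
- Section 9a puts the primary comparison at a time that is not on that schedule: "the response of SD and VT symptoms to sodium oxybate 40 min after administration, compared to placebo".
- Section 9a also says that oxybate effects "are obvious 30-45 min following drug intake and last approximately 3.5-4 hours".
- Section 12 has raters "count the voice breaks as well as to quantify harshness, breathiness, tremor, and hoarseness", which makes five measures. None is singled out for this analysis.
- Section 12 gives a percentage-change formula, but only for the alcohol challenge.

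The primary analysis is separate: a "linear mixed effect model with treatment (sodium oxybate and placebo) and treatment visits as interacting fixed effects".

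**The concern.** A Friedman test ranks two or more related conditions within each patient and asks whether their rank sums differ. Here the subtraction comes first, so treatment is no longer one of the conditions. Whatever remains to be ranked (times or measures) carries a different question from whether oxybate beats placebo.

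This is the only analysis in Section 12 labelled as measuring benefit, and it has its own significance threshold. A significant result could be reported as benefit when the test shows only that the difference was not the same at all times. Because the layout is not fixed, times, measures or treatments could each be chosen as the conditions after unblinding, and they answer different questions.

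**Working it through.** **The plan's own figure.** The plan gives no power or sample size for this test. Its only such figure, 22 patients (Section 5a), reproduces as an exact one-sided binomial test at 0.0125 if the unstated null rate is taken as 50%. The rule is to reject at 17 or more of 22; its size is 0.0085 and its power at 37/45 is 81.6%. The Friedman test plays no part in it.

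**Statistic.** For n patients, k conditions and rank sums R_j, Q = [12 / (n k (k+1))] Σ R_j² − 3n(k+1), on k − 1 degrees of freedom.

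**One difference per patient (k = 1).** Every rank is 1, so R_1 = n and Q = 12n²/(2n) − 6n = 0 on 0 degrees of freedom. There is no test.

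**Three post-dose differences (k = 3).** Q uses only within-patient ranks. Adding any constant c to all three of a patient's differences leaves the ranks, and hence Q, unchanged. This needs no distributional assumption.

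**Rejection rates.** The documents give no SD, effect size or correlation. The following are assumed: normal differences with SD 1, exchangeable correlation 0.3 / 0.5 / 0.7, α = 0.01, n = 22, and 20,000 simulated trials per cell for the 0.8 SD patterns.

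| Mean difference at 45, 180, 300 min (SD) | Drop by 300 min | Rejects (%) |
|---|---|---|
| 0.8, 0.8, 0.8 | 0 | 0.8-0.9 |
| 0.8, 0.8, 0.4 | 0.8 × 0.5 = 0.4 | 9 / 13 / 27 |
| 0.5, 0.5, 0 | 0.5 | 16 / 24 / 46 |
| 0.8, 0.8, 0 | 0.8 | 52 / 71 / 93 |
| 1.2, 1.2, 0 | 1.2 | 92 / 99 / >99 |

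Power follows the absolute change over time, which is benefit size times fraction lost. The stated duration of 3.5-4 h is 210-240 min, so a full or near-full fade by 300 min is the case that Section 9a implies.

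**What rejection means.** The pattern (0.8, 0.8, 0) minus 0.8 throughout is (0, 0, −0.8): no early effect and worsening at 300 min. By the constant argument the two must reject equally often. Direction is lost as well: at correlation 0.5, a fading benefit (1, 0.5, 0), a fading harm (−1, −0.5, 0) and a pattern averaging zero (−0.5, 0, 0.5) reject in 79%, 79% and 80%.

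**Other layouts the sentence might intend.**

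- *Two treatments ranked before subtraction (k = 2).* If s of n patients do better on oxybate, then R_1 = n + s and R_2 = 2n − s, and Q reduces to (2s − n)²/n, a sign test. At n = 22 it rejects for s ≥ 18 or s ≤ 4, with exact size 0.0043. For an assumed normal 0.8 SD difference its power is 49%, against 79% for the signed-rank test; at n = 35 the figures are 81% and 97%. Part of the gap is the sign test's small true size. The reading is valid, but it does not analyse the calculated difference.
- *Four times including pre-dose.* This responds to treatment. At n = 22, a constant post-dose shift of 0.8 SD gives 54 / 74 / 96% for benefit and the same for harm, so it has no direction.
- *Five measures.* This would rank a count of voice breaks against millimetres on a scale, so the ranks have no clear meaning.
- *Cohorts.* These contain different patients and cannot be repeated conditions.

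**The case against.** The strongest defence is that the test is not idle. Under the fade that Section 9a implies, it rejects in 52-93% of trials at an assumed 0.8 SD, and more for a larger benefit. The constant-benefit row is not what the plan expects, and nothing in the documents suggests late worsening. The signed difference is to be calculated, so its direction would be visible, and the mixed model tests treatment separately. The sponsor may also have meant to rank the two treatments, which is valid.

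Much of this stands, and it rules out stronger readings. A reader might infer that the test cannot detect anything, or that its power is unrelated to the size of the benefit; the table shows otherwise. The match between fading benefit and late worsening is algebra, not evidence that worsening is likely. A reader might also see a contradiction between the N/A in Section 10b and a secondary analysis in Section 12. There is none, since a secondary analysis can address the primary outcome; the N/A shows only that the definition is not there.

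What remains is that the p-value does not test the difference against zero. The plan names no estimate or interval for this quantity that would fill the gap. The two-treatment reading would need different wording from what is written.

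**Conclusion.** The concern holds in limited form. The conditions, the null and the definition of effect are missing. Applied to the quantity the plan calculates, the Friedman test is either undefined (one value per patient) or a test of variation over time. Those statements rest on algebra alone. The power figures rest on assumed normality, SD and correlation and are only illustrative.

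The impact is confined to this secondary analysis. A reader might infer that the trial's main conclusion is at risk; the documents do not support that, because neither the primary mixed model nor the 22-patient calculation uses this test. The change should be made, because it is cheap and prevents a significant result from being read as benefit.

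**What to change.** Before unblinding, amend Section 12 as follows:

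1. Rename the quantity *benefit difference*.
2. Define effect as change from the same-visit baseline on one named measure at one post-dose time, and state whether the change is absolute or percentage. Reconcile the 40 min primary time with the 45 min recording.
3. Within each group, test the within-patient difference against zero by a method that allows for period. One choice is a rank-sum comparison of the period 1 minus period 2 differences between the two sequences. A signed-rank test is an alternative if a period effect is assumed absent. State how ties and zeros are handled.
4. Report a Hodges-Lehmann estimate with a confidence interval. In the two-sequence comparison the shift is (τ + π) − (−τ + π) = 2τ, for treatment difference τ and period difference π, so it must be halved.
5. Keep Friedman only for a separately labelled question about change over time, with its conditions stated.

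The cost is a few sentences, with no new data or visits. One measure and one time must be fixed in advance, so the later recordings leave this particular test.

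The signed-rank option has two weaknesses. With assumed period shifts of 0.5 and 0.8 SD in the difference, its power at n = 22 falls from 79% to about 67% and 50%. It also assumes symmetry: with an exponential-shaped difference whose median is zero, it rejects in 2.6% (n = 22) and 4.5% (n = 35) of trials instead of 1%. The sign test keeps its level under such skew, at the cost of power.

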13. RISKS AND DISCOMFORTS AND MINIMIZATION OF RISKS

Risk is the probability and magnitude of harm or discomfort anticipated as a result of participation in the research.

Minimal risk means the probability and magnitude of harm or discomfort anticipated in the research are not greater in and of themselves than those ordinarily encountered in daily life or during the performance of routine physical or psychological examinations or tests.

a) Describe any risks of harm to subjects and/or anticipated discomfort(s) that are reasonably foreseeable, even if unlikely. Identify the safeguards you will put in place to minimize the occurrence of these risks and discomforts. Risks of harm and discomfort may include: physical harm/discomfort, psychological harm/discomfort, legal harm/discomfort, social harm/discomfort and economic harm.

Response: The daytime oral administration of sodium oxybate may entail the risks of developing dizziness, headache, somnolence, emotionality, and nausea as reported earlier (Frucht et al., 2005a; Frucht et al., 2005b; Arpesella et al., 2009). These side effects, however, have marked individual variability, are dose-dependent, observed within 10 minutes of the drug intake, and typically resolve within 30-40 minutes of dosing. Of these factors, dose is the most critical determinant of side effects. Our clinical experience with administering sodium oxybate in SD and VT patients suggests that the vast majority of these patients tolerate the 1.5 g dose without any side effects, and that, if they do develop side effects, these are extremely short lived.

There is a risk of intoxication from the alcohol that you will be given to drink. Symptoms of intoxication may include a feeling of drunkenness, slurred speech, lack of coordination and concentration, nausea, flushing of your face, or feeling hot.

There may be remote risk of loss of data. We will make every attempt to prevent the privacy and confidentiality risk by replacing personal identifying information with codes and by keeping encrypted digital data on the password-secured computer.

b) If applicable, describe any group harms (i.e. research that focuses on a specific group or population that if the results are disclosed, could harm the group as a whole).

Response: N/A

c) Describe any anticipated circumstances in which a "breach of confidentiality" associated with a mandated disclosure (e.g. reporting abuse to authorities) may occur as part of this study?

Response: N/A

d)	What risk classification (taking into consideration the probability and magnitude of harm) is appropriate for the proposed research?						
	□ Minimal Risk	X□Greater than Minimal Risk	□ Unknown				
e)	Explain why you feel	this category is appropriate based on	the definition above (if more than				

minimal risk, describe the likelihood and seriousness of such risks).

Response: The participants will receive, on separate visits, alcohol and sodium oxybate, which is a Schedule III controlled substance. Therefore, the risk is classified as Greater than Minimal Risk. However, the risk of serious adverse events is very low given the low dose of administered sodium oxybate and alcohol.

14. ALTERNATIVES

Describe any alternatives, to research participation available to potential patients.

Note: If there are no alternatives, other than "not participate" state so.

Response: The alternative is not to participate in the study.

15. BENEFITS

a) Will individual subjects have any direct benefits from the research? If subjects will not experience direct benefit, state so.

Response: It is possible that patients might benefit from participation in this trial, if sodium oxybate is developed as a symptomatic treatment for SD and VT.

b) Explain the potential benefits to science, and/or society as a result of this research.

Response: Possible benefits from participation in this study include learning whether or not sodium oxybate might help improve symptoms of SD and VT.

c) If this study is more than minimal risk, explain how the risks are minimized in relation to the anticipated benefits of the study:

Response: N/A

16. DISSEMINATION OF RESULTS

a) Describe any plans to share research results with subjects, EITHER individual results and/or aggregate results. If there are no plans to share results, explain why this is not feasible, appropriate, or applicable to this research.

Response: The results of the studies will be shared with the subjects upon the publication of the findings. At that time, the subjects who participated in each research study will receive a letter in lay language explaining the details of findings as published in a peer-reviewed journal.

b) How will results be published, and in what form (newsletter to subjects, peer-reviewed publications)?

Response: The results of the studies will be shared with the subjects upon the publication of the findings. At that time, the subjects who participated in each research study will receive a letter in lay language explaining the details of findings as published in a peer-reviewed journal.

17. INCIDENTAL FINDINGS

If there is the possibility that study procedures may identify incidental findings of medical importance to a subject and/or the subject's family (e.g., genetic studies, imaging studies, studies that conduct routine blood tests, etc.), describe the plan for reporting any incidental findings (e.g., study physician will discuss with subject/subject's PCP, genetic counseling). In addition, researchers may uncover evidence of child, domestic, or elder abuse, which require reporting to authorities. Please describe the plan for reporting such findings.

Response: In case of incidental findings of clinical relevance, the patient or his/her referring physician will be notified for a follow up.

18. PRIVACY/CONFIDENTIALITY

NOTE: MEE researchers must adhere to MEE Information Security Policies and Procedures when designing their research protocols. The HSC evaluates the collection, use and storage of data and may require additional safeguards. For example, the HSC may require a Certificate of Confidentiality for research projects that collect personally identifiable, sensitive information.

a) Describe the plan for protecting the privacy and confidentiality of subjects throughout the research (e.g., limited access to medical records and identifiable study data, data security procedures consistent with MEE Information Security Policy).

Response: Every effort will be made to respect and maintain the confidentiality of study participants according to current legal requirements and as required by the Federal Privacy Act.

All communications with the subject, such as consent, screening, phone messages, mail, etc., and study related information shared by a patient will be kept strictly private at all times. Consenting and screening of patients will be done in a private room, with only research members present. Subjects will be informed that they may choose not to answer a specific question about their medical history, however, this may present one of the reasons for exclusion as determined by a research team. Data security procedures will be consistent with MEEI Information Security Policy.

Confidentiality with respect to names, medical, treatment and family information, examination findings, and laboratory findings will be maintained. The patient's name is present in the patient medical record. When extracting data from the patient medical record for research purposes, the information may contain identifiers for the purpose of linking the extracted information back to additional data in the source document.

In the event that clinical information (including examination findings, laboratory findings, family history, medical and treatment information) or data derived from this information is presented at scientific meetings, for teaching, or for publication, the subject's name or the family name will not be disclosed. In the event that videotapes, audiotapes, and/or photographs are used at scientific meetings, for teaching, or for publication, the subject's name or the family name will not be disclosed, but the subject's face may be visible.

b) Where will you store research data, signed informed consent forms, and assent forms to maximally protect privacy and confidentiality?

Response: All research data will be stored on password-protected and secured network attached servers in the PI's laboratory. Medical information and questionnaires will be stored in the locked file cabinets in the PI's laboratory.

c) Please provide the plan for destroying identifiers (at the earliest opportunity as consistent with the research plan) or provide a health or research justification for retaining identifiers. For protocols subject to future and secondary data analysis, provide justification for not destroying identifiers permanently and explain plans for future use (i.e., establishment of a data or specimen repository).

Response: Scans and blood samples will originally have the identifiers, which will be removed before the data analysis will be conducted. All scans and blood samples will receive a unique research code when the subject identifiers are removed. The list linking the code to the subject will be stored on the PI's password-secured server. All research data will receive a unique research code when the subject identifiers are removed. All video and audio files will be removed from the recording device immediately after the recording and transferred to the secured, encrypted server. All video and audio files will be de-identified before data analysis.

d) Will you obtain samples/data from outside sources? Please specify from whom you will obtain samples and what information you will obtain with each sample. Please note that a Material Transfer Agreement may be required for this research activity. (Contact Research Administration for instructions.)

Response: N/A

e) Will samples from MEE be provided to outside sources? Please specify to whom you will provide MEE samples and what information/data will accompany each sample. Please note that that a Material Transfer Agreement will be required for this research activity.

Response: De-identified voice and speech recordings will be shared with [name] at the University of Queensland via Partners Dropbox Business account. [name] will be fully blinded to the identity of participants and to their time points of participation in this study. She will be involved in the analysis of these data according to the data analysis protocol described above.

19. DATA and SAFETY MONITORING PLAN (DSMP)

a) If the research is no more than minimal risk, describe any provisions in place to ensure the safety of participants. In minimal risk studies, there is always the risk of loss of confidentiality and privacy. However, minimal risk studies involving blood draws, imaging, and eye exams may have risks associated with the study procedure.

Response: Please see response under 13a.

b) If the research is more than minimal risk, please provide a detailed data and safety monitoring plan (DSMP). Include the individual(s) or group responsible for data and safety monitoring (e.g., PI, specific members of the study team, independent monitor(s), a convened Data and Safety Monitoring Board - DSMB). Please see the guidance document in IRBNet for developing a DSMP.

Response:

Detailed Monitoring Plan, Data Management and Quality Assurance Plan, and DSMB Charter are enclosed as separate documents.

Because of a drug administration, the DSMP will be followed. The PI will be responsible for internal data review to verify adherence to the protocol, local regulations on the conduct of clinical research,

and ensure completeness, accuracy, and consistency of the data. [name] will serve as an external monitor and will perform external monitoring, including the rates of recruitment, ineligibility, noncompliance, protocol violations and dropouts; completeness and timeliness of the data; accrual within important subsets according to the Monitoring Plan. [name] and [name] will serve as members of the Data and Safety Monitoring Board and will be responsible for the review of safety and efficacy of data and the assessment of the risk to the research subject's health and well-being according to the DSMB Charter. Specific items for monitoring will include the integrity of research records in compliance with institutional policies, adverse events, subject compliance with the protocol, and subject drop-out. The External Monitor and DSMB will be responsible for providing recommendations for the study continuation, amendment, or discontinuation.

Internal monitoring by the PI will be conducted on a monthly basis or as frequent as needed; external monitoring by [name] will be conducted after the enrollment of each 10 subject; DSMB monitoring will be performed on a bi-annual basis.

Adverse effects will be recorded in the research chart and adverse events log and reported to the MGB IRB in accordance with Federal policies and as described in the institutional policy on Unanticipated Problems Involving Risks to Subjects or Others. The NCI CTC (Common Toxicity Criteria) will be used to evaluate adverse events. Research charts will be reviewed for all recorded information about the research procedures completed and documented adverse events.

The study will be terminated when an adequate amount of data is collected. If a serious unexpected adverse event occurs that might indicate undue risk and could not be prevented for future participants, then the study would be stopped.

Please see enclosed the detailed DSMP.

c) Provide information related to the expertise and qualifications of the individual(s) and/or groups listed above relative to monitoring.

Response: [name] has research and clinical expertise in SD and VT and has conducted the open-label study of sodium oxybate in these disorders according to a very similar research protocol. [name] is an expert speech-language pathologist who has a long-standing interest in SD and VT research. [name] is an otolaryngologist who has special interests in the development of novel methods for cochlear drug delivery and understanding mechanisms of noise- and age-related hearing loss. [name] is a Clinical Research Coordinator II at the MGH Department of Psychiatry, Division of Neuropsychiatry and Neuromodulation. She has relevant experience and training in the conduct of human research and is familial with this protocol and procedures.

d) Please explain how data and safety monitoring activities for this study will be documented (e.g., a monitoring log kept in the regulatory binder).

Response: All research procedures and research documentation will be reviewed by the PI and her research team on a monthly basis or as frequent as needed for their completeness, accuracy, validity and integrity of the data in adherence to the IRB-approved protocol according to the Data Management and Quality Assurance Plan. The External Monitor (after each 10 subjects are recruited) and DSMB (bi-annually) will help the PI maintain a high level of ethical, scientific, technical and regulatory quality in all aspects of the study according to the procedures described in the Monitoring

Plan and DSMB Charter. During this three-tiered review, the informed consent, subject recruitment and follow-up, study allocation, subject compliance with the study procedures, Adverse Event documentation and reporting, and quality of data will be monitored.

e) Explain if any individual involved in monitoring has relationships with sponsors, organizers or researchers, conducting the study, and if applicable, describe the nature of these relationships.

Response: No relationship with sponsors or organizers. The statement of conflict of interest from the external monitor and DSMB members will be obtained prior to each monitoring meeting.

f) If applicable, describe the process for communication of Data and Safety Monitoring Board reports to the investigator and to the HSC.

Response: Following each DSMB meeting, a written report will be generated that will include the findings and recommendations of the DSMB. The report will be sent to the PI and, in case of serious adverse events and/or protocol deviations, to the MGB IRB. See details in the Data and Safety Monitoring Board Charter.

